## 4 Study Population

### 4.1 Inclusion Criteria

All tumor size and location-related eligibility criteria listed below will be independently verified by the Sponsor or their designee prior to patient enrollment.

A patient will be eligible for inclusion in the study if he/she meets all the following criteria prior to Day 0 (ie, catheter placement for PVSRIPO infusion) and after catheter placement, where specified:

1.  $\geq 18$  years of age.
2. Actively growing recurrent supratentorial glioblastoma confirmed by biopsy by the site's neuropathologist or designee.
  - o Recurrent glioblastoma histologically confirmed within 6 weeks prior to PVSRIPO infusion will not require a biopsy to confirm active tumor prior to catheter placement. However, biopsy confirmation of glioblastoma must be provided prior to PVSRIPO infusion if histological confirmation is not completed within 6 weeks prior to catheter placement.
  - o For the purpose of this protocol, "recurrence" is defined by either progression of primary glioblastoma or transformation from a lower grade to a higher grade. Note that in the case of transformation, this change must be confirmed via histology by site pathologist.
3. Enhancing lesion  $\geq 1$  cm shortest diameter to  $\leq 5.5$  cm longest diameter in all planes; occurrence within the prior resection cavity should not contribute to the longest diameter measurement.

4. Before catheter placement based on screening MRI and at the time of catheter placement via CT prior to infusion, neurosurgical investigator must confirm both tumor location ( $\geq 1$  cm from eloquent brain) as well as placement of infusion catheter within or through the progressive enhancing tumor is feasible and at a safe distance relative to eloquent brain function, with the tip of the catheter being placed:
  - a. Within the enhancing portion or in the vicinity of enhancement of target lesion (ie, infiltrative disease)
  - b.  $\geq 0.5$  cm from ventricles
  - c.  $\geq 1$  cm deep into the brain
  - d.  $\geq 0.5$  cm from the corpus callosum
5. First or second relapse supported by MRI or CT scan; relapse is defined as progression following initial/prior therapy(ies).
6. Failed previous first line therapy: maximum surgical resection and RT (plus concomitant chemotherapy followed by maintenance chemotherapy if unknown or MGMT promoter). Patients who begin but do not complete chemotherapy/RT may still be considered for eligibility at the discretion of Sponsor.
7. KPS  $\geq 70$  at screening and baseline.
8. Undergone prior vaccination against PV and received a boost immunization with trivalent IPOL® (Sanofi-Pasteur SA) at least 1 week, but less than 6 weeks, prior to administration of PVSRIPO (within 6 months of PVSRIPO retreatment). Note: Patients who are unsure of their prior vaccination status/who have not been vaccinated must provide proof of vaccination and/or evidence of anti-PV immunity prior to enrollment, as applicable.
9. Ability to safely discontinue anti-coagulant therapy(ies) prior to biopsy/catheter placement, as required per site/surgical guidelines, in the opinion of the investigator.
10. Hemoglobin  $\geq 9$  g/dL prior to biopsy/catheter placement.
11. Platelet count  $\geq 100,000/\mu\text{L}$  (unsupported);  $\geq 125,000/\mu\text{L}$  (can be supported via platelet transfusion) at biopsy/catheter placement and/or with a Sponsor-approved bone marrow stimulant/colony stimulating factor, eg, romiplostim).
12. ANC  $\geq 1000/\mu\text{L}$  prior to biopsy/catheter placement.
13. Creatinine  $\leq 1.2 \times \text{ULN}$  prior to biopsy/catheter placement.
14. Total bilirubin, ALT, AST, ALP  $\leq 2.5 \times \text{ULN}$  prior to biopsy/catheter placement.
15. PT and aPTT  $\leq 1.2 \times \text{ULN}$  prior to biopsy/catheter placement.
16. If undetectable ATT IgG at screen, Tdap booster vaccine  $> 1$  week prior to biopsy/catheter placement.
17. Patients must be willing and able to understand and provide written informed consent.

#### 4.2 Exclusion Criteria

A patient will not be eligible for inclusion in this study if he/she meets any of the following criteria prior to Day 0 (PVSRIPO catheter placement):

1. Received prior therapy with an anti-PD-1, anti-PD-L1, anti-PD-L2, anti-CD137, or anti-CTLA-4 antibody (including ipilimumab or any other antibody or drug specifically targeting T-cell co-stimulation or checkpoint pathways)  $\leq$  12 weeks prior to PVSRIPO infusion (Note: does not apply for patients treated with pembrolizumab under this protocol who are eligible for PVSRIPO retreatment). Patients who had previously permanently discontinued any anti-PD-1 or PD-L1 therapy due to severe or life-threatening immune-related AE are excluded.
2. Excluded are:
  - a. Neoplastic lesions in the brainstem, cerebellum, or spinal cord
  - b. Radiological evidence of active/growing multifocal disease: no size increase  $> 0.5$  cm in any direction of any other enhancing non-target lesions present at baseline confirmed via most recent, prior, consecutive MRIs at least 3 months apart. However, two lesions connected by T2 flair are not excluded.
  - c. Tumors with  $\geq 1$  cm of contrast-enhancing tumor component crossing the midline (crossing the corpus callosum)
  - d. Extensive subependymal disease: multiple lesions or lesions covering  $> 50\%$  of subependymal space. Tumor touching subependymal space allowed.
  - e. Extensive leptomeningeal disease: multiple lesions or lesions covering  $> 50\%$  of leptomeninges. Tumor touching leptomeninges allowed.
3. Has received systemic immunosuppressive treatments other than systemic corticosteroids (eg, methotrexate, chloroquine, azathioprine) within six months of PVSRIPO infusion.
4. Requires treatment with high dose systemic corticosteroids, defined as dexamethasone  $> 4$  mg/day or equivalent, within 2 weeks of PVSRIPO infusion.
5. Prior interstitial brachytherapy, implanted chemotherapy, stereotactic radiosurgery or therapeutics delivered by local injection or CED, including PVSRIPO (except for qualifying patients being retreated with PVSRIPO within this trial).
6. Pregnant and/or breast feeding female; patient/female partner of childbearing potential who is unwilling to utilize protocol-defined acceptable form of contraception for duration of study.
7. Impending/life-threatening cerebral herniation syndrome, per neurosurgeon/designate.
8. Severe, active co-morbidity, defined as follows:
  - a. Infection requiring IV treatment/unexplained febrile illness ( $T_{max} > 99.5^{\circ}\text{F}/37.5^{\circ}\text{C}$ )
  - b. Known immunosuppressive disease/human immunodeficiency virus infection
  - c. Known active hepatitis B or C infection via positive viral DNA or RNA, respectively
  - d. Unstable or severe intercurrent medical conditions such as severe heart disease (New York Heart Association Class 3 or 4)
  - e. Known lung disease with forced expiratory volume in 1st second of expiration  $< 50\%$
  - f. Uncontrolled diabetes mellitus (eg, hemoglobin A1C level  $> 7.0\%$  with treatment)
  - g. History of other malignancy requiring active treatment within 2 years of biopsy/catheter placement with the exception of those with a negligible risk of

metastasis or death (eg, resected cutaneous basal cell carcinoma, or other cancers with 5-year OS of > 90%)

9. Known albumin allergy.
10. Uncontrolled unexplained bleeding and/or hemoptysis within 4 weeks of planned PVSRIPO infusion.
11. Inability to undergo brain MRI with and without contrast. History of severe/anaphylactic reaction to gadolinium contrast agent is excluded. Mild allergy (eg, rash) acceptable with prophylactic acetaminophen and diphenhydramine.
12. History of neurological complications due to PV infection.
13. Not recovered from toxic side effects (alopecia acceptable) and/or no current or prior tumor treatments within the following timeframe relative to biopsy/catheter placement:
  - a. Chemotherapy or bevacizumab  $\leq$  4 weeks (except for nitrosourea [6 weeks] or metronomic dosed chemotherapy such as daily temozolomide, etoposide or cyclophosphamide [1 week])
  - b. Tumor treating fields  $\leq$  7 days
  - c. RT of brain  $\leq$  12 weeks, except for progressive disease outside of the radiation field or 2 progressive scans at least 4 weeks apart or histopathologic confirmation
14. History of agammaglobulinemia.
15. Known hypersensitivity to pembrolizumab, or any components of pembrolizumab.
16. Active autoimmune disease requiring systemic immunomodulatory treatment within the past 12 months; physiologic replacement therapy (eg, thyroxine, insulin, or physiologic corticosteroid replacement therapy for adrenal or pituitary insufficiency) is not considered a form of systemic treatment.

#### **4.2.1 Additional Exclusion Criteria per Sponsor or Designee: Notification of Enrollment Goal Met**

1. The study is targeting balanced enrollment of patients with and without any prior anti-angiogenic or anti-VEGF-targeted agent uses (eg, bevacizumab, cediranib, afibbercept, vandetanib, cabozantinib, sunitinib). As such, once 50% of planned patients (ie, 15 patients) are enrolled into either group, enrollment into the other group may end and future patients with that criterion may not be eligible. For example, after 15 patients who received prior anti-VEGF therapy are enrolled and treated with PVSRIPO and  $\geq$  1 dose of pembrolizumab, enrollment may be limited to only patients without prior anti-VEGF therapy use.
2. The study is targeting enrollment of  $\geq$  50% of patients who failed a prior chemotherapy regimen. If the study enrolls 40% of subjects who did not fail a prior chemotherapy regimen (ie, 12 of the first 30 subjects had no prior chemotherapy, which is not required if MGMT promotor unmethylated), enrollment into this group may be halted and future patients who did not have any prior chemotherapy may not be enrolled.

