There will be 2 patient strata at enrollment: the first, based on receipt of any prior anti-angiogenic or anti-VEGF targeted agents (eg, bevacizumab, cediranib, afibbercept, vandetanib, cabozantinib, sunitinib, etc.) and the second, based on prior chemotherapy use. The size of the stratum for VEGF targeted agents will be capped at  $\leq 50\%$  of the total population enrolled (ie, do not want  $> 50\%$  of the patients enrolled to have failed prior VEGF targeted therapies). The size of the stratum for prior chemotherapy use will be  $\leq 50\%$  of the total population enrolled, regardless of MGMT promoter methylation status (ie, want  $> 50\%$  of the patients receiving the combination to have failed prior chemotherapy use). Enrollment and eligibility criteria will be monitored to meet these goals. Data will be analyzed together and separately, by these strata.

Responses may also be summarized in by subgroup analyses including but not limited to baseline NANO score and KPS, prior bevacizumab and chemotherapy or other tumor treatment use/failure, extent of surgery at diagnosis (GTR, STR), MGMT promoter methylation status and/or other tumor genetic factors at diagnosis and baseline, lesion cross-sectional area at baseline, time from initial diagnosis to baseline, number of prior progressions, age, and sex.

For any informal summary comparisons of safety or efficacy relative to PVSRIPO, pembrolizumab or other ICI alone or in combination from other data sources, both the overall and per-protocol populations may be considered.

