### **6. CHANGES IN THE PLANNED ANALYSES**

1. Day 0 is the earliest day that study drug is initiated but will be designated as Day 1 based on implementation standards for the analysis.
2. Central imaging review was not completed; therefore, results from this will not be presented.
3. The following analyses will not be completed:
  - a. Durable radiographic response (DRR)
  - b. Duration of disease control (DDC)
  - c. Progression-free survival (PFS)
  - d. Analysis of Per-Protocol population
  - e. Analyses based on participant strata (prior anti-VEGF agents, prior chemotherapy use)
  - f. Analyses on the efficacy set and PP set for the following subgroups: baseline NANO score, KPS, prior bevacizumab and chemotherapy or other treatment use/failure, extent of surgery at diagnosis, MGMT promoter methylation status and/or other tumor genetic factors at diagnosis and baseline, lesion cross-sectional area at baseline, number of prior progressions, age, gender.

- g. Landmark survival at month 24
- h. Exploratory analyses including analysis of efficacy based on modified iRANO criteria in Section 8.4.6.1, Table 3 of the protocol, identification of biomarkers of anti-tumor response to lerapolturev following by pembrolizumab or assessment of patient reported outcomes
- 4. The entire anticipated sample size of patients was not enrolled.

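### Two enrolment-cap rules are wrong as written: the anti-VEGF rule closes the under-filled group, and the chemotherapy cap contradicts its own explanation

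*Protocol*

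**What the plan says.** **Anti-VEGF, Protocol 4.2.1 item 1.** The goal is stated first: "The study is targeting balanced enrollment of patients with and without any prior anti-angiogenic or anti-VEGF-targeted agent uses". The trigger follows: "once 50% of planned patients (ie, 15 patients) are enrolled into either group". The action is that "enrollment into the other group may end and future patients with that criterion may not be eligible". The example in the next sentence takes 15 treated patients with prior anti-VEGF therapy and concludes that "enrollment may be limited to only patients without prior anti-VEGF therapy use".

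**Anti-VEGF, Protocol 8.4.6.** The stratum with prior VEGF-targeted agents is capped at 50% of those enrolled. No cap is set on the stratum without them.

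**Chemotherapy, Protocol 4.2.1 item 2.** The target is at least 50% of patients with a failed chemotherapy regimen. The stopping trigger reads "If the study enrolls 40% of subjects who did not fail a prior chemotherapy regimen", illustrated as 12 of 30; enrolment of that group may then be halted.

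**Chemotherapy, Protocol 8.4.6.** "The size of the stratum for prior chemotherapy use will be" at most 50% of the total enrolled. The parenthesis explains this as wanting more than 50% "of the patients receiving the combination to have failed prior chemotherapy use".

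**SAP.** Section 3.2.1 uses no strata. Section 6 item 3 lists among the analyses that will not be done "Analyses based on participant strata (prior anti-VEGF agents, prior chemotherapy use". Item 4 of the same section says that the planned sample size was not reached.

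**The concern.** Section 4.2.1 is headed as additional exclusion criteria, so once a cap is met these sentences decide who is turned away. The anti-VEGF sentence names the wrong group: enforced as written, it produces the imbalance it was meant to prevent. The chemotherapy sentence in 8.4.6 caps the group that its own explanation wants in the majority.

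The primary ORR is a single pooled proportion, with 7/61 from the Phase 1 study as its reference in the sample-size section. If response differs by prior treatment, the mix of patients shifts that proportion. Protocol 8.4.6 planned to analyse the data both together and by these strata, which would have let a reader see the mix at work. The SAP removed that analysis.

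**Working it through.** **1. The plan's own figure.** Inputs (Protocol 8.1, SAP 3.1): N = 30, reference ORR 0.11, target ORR 0.31, two-sided 0.05. I used an exact binomial test with an upper tail of at most 0.025.

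- P(X ≥ 7 | 30, 0.11) = 0.0407, too large. P(X ≥ 8 | 30, 0.11) = 0.0135, so the rule is at least 8 responses.
- Power = P(X ≥ 8 | 30, 0.31) = 0.757.

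This agrees with the stated figure of more than 75%. The calculation does not use the caps.

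**2. Anti-VEGF counts.** Let k be the number with prior anti-VEGF therapy among 30, with each rule enforced.

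| Rule | Possible k | Share |
|---|---|---|
| 4.2.1 example, applied to either group | 15 | 50% |
| 8.4.6, cap on exposed patients only | 0 to 15 | 0 to 50% |
| 4.2.1 sentence, exposed group fills first | 16 to 30 | 53 to 100% |
| 4.2.1 sentence, unexposed group fills first | 0 to 14 | 0 to 47% |

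In the third row the unexposed group closes with at most 14, so k ≥ 30 − 14 = 16, above the 8.4.6 ceiling. In the fourth row the exposed group closes with at most 14. The sentence never yields 15:15. As an illustration, if 8 unexposed patients are in when the exposed group reaches 15, then k = 30 − 8 = 22, or 73%.

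**3. Chemotherapy counts at N = 30.**

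| Statement | Implied count |
|---|---|
| 4.2.1 item 2, goal | at least 15 failed |
| 4.2.1 item 2, trigger enforced | at most 12 not failed, so at least 18 failed (60%) |
| 8.4.6, cap | at most 15 users |
| 8.4.6, explanation | at least 16 failed |

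Everyone who failed chemotherapy had used it, so failures cannot exceed users. At most 15 users and at least 16 failures are incompatible on a common base. The cap also points the opposite way from 4.2.1 item 2, which restricts patients without chemotherapy failure.

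The two halves of the 8.4.6 sentence do name different denominators: all enrolled, and those receiving the combination. With 32 enrolled, 16 users (50%) and 16 failures among 30 combination patients (53%) could coexist, but only if both extra patients were non-users. The parenthesis is offered as a restatement of the cap, so this is not its meaning.

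**4. Counting base.** Section 4.2.1 counts patients enrolled in its trigger but patients given both agents in its example. Section 8.4.6 counts the total enrolled. These differ because patients who receive PVSRIPO alone are replaced (Protocol 4.5).

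**5. Effect on ORR, by assumption only.** The documents give no ORR by stratum. If the stratum rates differ by d, moving from 15 exposed to k exposed shifts the pooled ORR by d × (k − 15)/30.

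- d = 0: no shift.
- d = 10 points: k = 22 gives 10 × 7/30 = 2.3 points; k = 30 gives 5.
- d = 20 points: k = 22 gives 4.7 points; k = 30 gives 10.

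With assumed rates of 36% unexposed and 26% exposed, the chance of at least 8 of 30 responses is 0.90, 0.76 and 0.54 at k = 0, 15 and 30. These figures show how the result depends on assumed inputs. They do not estimate anything about this trial.

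**The case against.** The strongest reply is that the intent is clear and the rules are mostly soft. For anti-VEGF, the balance goal, the example and the 8.4.6 ceiling all agree, and only one phrase is out of line. Every closure in 4.2.1 is permissive, so the sponsor would have to act against its own goal and example to do harm. This stands, and it makes the fault a drafting error. It does not excuse leaving a wrong sentence in an exclusion rule. The 8.4.6 chemotherapy sentence has no example to correct it, although its explanation and 4.2.1 item 2 both point to a majority with failed chemotherapy.

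Four further inferences are tempting, and the documents do not support them.

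- *That the 40% trigger contradicts the 50% goal.* It is stricter than the goal and guarantees it.
- *That capping both anti-VEGF groups at 15 conflicts with the one-sided cap in 8.4.6.* Closing each full group at 15 satisfies that cap.
- *That treating patients without chemotherapy failure as patients without prior chemotherapy creates a materially different group.* Inclusion criteria 5 and 6 require relapse and failed first-line therapy, so the two largely coincide. The exception is sponsor-approved patients who did not complete chemotherapy.
- *That the report could not show any effect.* SAP Table 14.1.3.2 summarises prior therapy in the Safety Set, and Listings 16.2.4.7.1 and 16.2.6.2 give prior systemic therapy and response by participant. What is missing is a planned table of ORR by either factor.

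**Conclusion.** Two rules are wrong as written: the closing action in Protocol 4.2.1 item 1 and the direction of the chemotherapy cap in 8.4.6. The varying counting base is a lesser fault. These conclusions rest on the text and on counting at N = 30.

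A reader might go further and infer that the trial's ORR depends on which sentence was applied, or that case mix could move it by a stated number of points. The documents do not support that. They give no ORR by stratum and no case mix for the Phase 1 reference group, so neither the size nor the direction of a shift can be found. They do not say that either anti-VEGF group reached 15, or that the group without chemotherapy failure reached 12, and enrolment ended below plan. The stated power reproduces and is unaffected.

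**What to change.** **Protocol 4.2.1 item 1:** change *the other group* to *that group*, so that the rule matches its example.

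**Protocol 8.4.6:** apply the chemotherapy cap to the stratum without prior chemotherapy failure, and reconcile its percentage with 4.2.1 item 2.

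**Both sections:** use one counting base, namely patients given PVSRIPO and at least one dose of pembrolizumab, as the 4.2.1 example already does.

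**SAP:** report the realised mix of both factors in the efficacy set, and add to Table 14.2.1.1 a descriptive ORR with exact 95% interval by each factor.

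Since enrolment ended short of plan, new protocol wording cannot change who entered. It corrects the record and matters if the study is expanded, which Protocol Section 3 allows. The SAP additions are the part that still affects the report.

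The cost is wording in two protocol sections and a few table rows. Prior systemic therapy and response are already collected, so no new data are needed. The drawback is imprecision: even 8 of 30 has an exact 95% interval of 12.3% to 45.9%, and strata of about half that size or less will generally be wider. The rows must be labelled descriptive.

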#### **4.3 Patient Identification (ID)**

Patients will be identified by a unique numeric patient ID assigned at time of screening.

#### **4.4 Removal, Replacement, or Early Withdrawal of Patients from Therapy or Assessment**

Participants may voluntarily withdraw from the study at any time.

The Investigator may also withdraw a participant from the study at any time based on his/her discretion. Reasons for Investigator-initiated withdrawal may include, but are not limited to the following:

- Progressive disease as documented by MRI, physical examination, or tissue sample at any time after the completion of therapy requiring treatment with non-protocol therapy (in keeping with the criteria outlined in **Table 3**)
- Pregnancy
- Upon request of the participant
- If, in the Investigator's medical judgment, further participation would be injurious to the participant's health or wellbeing
- Development of intolerable symptoms
- Protocol deviation
- Non-compliance of the participant
- Administrative issues

#### **4.5 Handling of Withdrawals**

Participants withdrawing from the study prior to receiving PVSRIPO infusion, either voluntarily or due to ineligibility, will be considered non-evaluable in all but the screening analysis set (see **Section 8**); these patients will be replaced. Minimal information will be retained in the study database for screen failures.

Patients who are treated with  $> 4$  mg/day dexamethasone (or equivalent) prior to receiving the first dose of pembrolizumab and patients who do not receive  $\geq 1$  dose of pembrolizumab after PVSRIPO will also be replaced and will not contribute to the PVSRIPO plus pembrolizumab (ie, combination) datasets. These subjects will continue to be followed for safety and efficacy and will be summarized separately.

If patients do not enter the voluntary follow up period, all information as described at the next scheduled study visit if <11 weeks after PVSRIPO treatment or at the End of Study (EOS) visit, should be obtained, if possible and as applicable.

Handling of early withdrawals for analyses are outlined in [Section 8](#).

